# 4 Study Design and Endpoints

# 4.1 Description of Study Design

The proposed study is a phase I/II, single-center, double-blind, randomized proof-of-concept study designed to assess safety and feasibility in the AUD+PTSD/subthreshold PTSD population and contrast effects of CBD treatment to those of placebo on drinking-related outcomes and PTSD symptoms. We will evaluate the safety of an extended daily CBD treatment regimen in an AUD+PTSD/subthreshold PTSD population, measure resulting plasma and CBD and THC levels, generate preliminary data on the impact of CBD on alcohol consumption and PTSD symptoms, assess the effect of CBD on a human laboratory measure of traumatic-stress induced craving and neuropsychological measures relevant to AUD and PTSD/subthreshold PTSD, and assess the effect of CBD dosing no plasma anandamide levels.

150 participants are expected to be enrolled in the study prior to screening and randomization. Following screening and baseline assessments, 48 participants who fully meet study criteria are expected to be randomized in a 5:3 ratio to receive either 600mg CBD/day (PO) or placebo respectively for 6 weeks (N=30 participants on CBD and N=18 participants on placebo). This dose was selected to optimize anxiolytic affects to target stress induced alcohol craving. Assessments of drinking and PTSD related outcomes will be completed at baseline and weekly over 6 weeks of treatment, with an assessment one week following the end of treatment. The human laboratory task and assessments of cognitive function will be completed at baseline and at the end of 6 weeks of treatment. Measurement of circulating levels of CBD, THC, and THC metabolites (Delta-9 THC, 11-Hydroxy Delta-9 THC and Delta-9 Carboxy THC) will be obtained from CBD-treated participants at baseline, 45 minutes, 1 day, 1 week, 2 weeks, 4 weeks, 6 weeks, and 7 weeks after treatment with the first dose of CBD vs. placebo. Anandamide levels will be obtained from both CBD- and placebo-treated participants at the aforementioned time-points.

Outcomes will include drinking outcomes; PTSD symptoms; responses to personalized trauma and alcohol scripts designed to elicit stress- and cue-induced craving and anxiety; cognitive function; circulating levels of CBD, THC and anandamide and safety measures (adverse events, cognitive and motoric function), and psychological domains relevant to AUD+PTSD/subthreshold PTSD including self- reported craving, depression, and anxiety across 6 weeks of treatment and one week following the end of treatment.

Voice-markers: High-fidelity audio recordings from in-person or remote sessions of clinical interviews will be collected at screening. The audio recordings will be encrypted and transferred via secure transfer methods to a HIPAA compliant specialized entity for quality control and voice-makers analyses. If the participant gives their consent, the collected audio recordings will be used to examine voice-markers as a function of a patient's AUD and PTSD status and to develop assessment models that use lexical and prosodic features to classify a patient's AUD and PTSD status. All the recordings will be de-identified and labeled with a unique study code number for each participant in the study. Study personnel of the HIPAA compliant specialized entity receiving voice-marker data will not have access to link participants' study code to any identifying information collected throughout the study. These personnel will not be able to re-identify study participants associated with the respective data using the unique identifiers. If the recorded audio data has any identifying information embedded in the recordings, that information will be removed by study staff, who will review each audio file and delete any PHI before the file is sent to the specialized lab. Once the files are received, the specialized lab will double check the data for any PHI and if found, this will be removed prior to the data being used.

# 4.2 Study Endpoints

# 4.2.1 Primary Study Endpoints

The primary study endpoint for alcohol use will be number of drinks per day assessed by the Time Line Follow Back methodology [78]. The primary study endpoint for PTSD symptoms will be the PCL-5 total score. Safety will be assessed by collection of adverse events at all visits after treatment is initiated in addition to LFTs collected at screening, as well as weeks 2, 6, and 7 to assess the liver function during and after treatment

#### 4.2.2 Secondary Study Endpoints Secondary Alcohol use endpoints

Secondary efficacy endpoints are the percent carbohydrate-deficient transferrin (CDT); the percentage of heavy drinking days (four or more drinks for women or five or more drinks for men per drinking day) averaged for each treatment week; weekly average severity of alcohol craving assessed by the Penn Alcohol Craving scale [79]; weekly percentage of very heavy drinking days (8+/10+ drinks per day for women and men respectively); weekly percentage of days abstinent; weekly percentage of subjects with no heavy drinking days, and weekly percentage of subjects that are 'present and clean', i.e. present to provide breath alcohol levels (BAC) and have a BAC of zero [80].

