# 3 Study Enrollment and Withdrawal

# 5.1 Inclusion Criteria

In order to be eligible to participate in this study, an individual must meet all of the following criteria:

- 1. Males and females age 18-70
- 2. DSM-5 diagnosis of moderate or severe AUD

3. DSM-5 diagnosis of PTSD with Clinician Administered PTSD Scale (CAPS-5) OR subPTSD diagnosis (meeting criterion A, F, G, H and at least 6 symptoms across any criteria B-E) with Clinician Administered PTSD Scale (CAPS-5)

4. Able to provide voluntary informed consent

5. At least 4 heavy drinking days (4 or more drinks per day for a woman, 5 or more drinks per day for a man) in the 30 days prior to screen

6. If of childbearing potential (male or female), are willing to use approved form of contraception from screening for duration of the trial

- 7. Able to provide at least two locators
- 8. Endorse desire to cut down or stop drinking
- 9. Agrees to abstain from all other cannabinoid use for the duration of the study
- 10. Confirms they are reliably domiciled

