### 20.3 Description of Statistical Methods

### 20.3.1 General Approach

We recognize that the relatively small sample sizes proposed in the RCT are not likely to produce statistical significance, unless the effect sizes are remarkably high. We will carry out a full Mixed Model Repeated Measures (MMRM) statistical analysis in case CBD does perform so well. However, the main focus of the statistical analysis of the results of the trial will be to characterize the effect sizes and response rates across the various measurement domains and the profiles of individuals who are treatment successes. The intent to treat (ITT) population will contain all randomized patients who receive at least one dose of double-blind study medication and from whom at least one post-baseline (B1) efficacy measurement is obtained while on study medication. The efficacy analysis will be based on the ITT population. Two-sided hypothesis testing will be utilized. Tests with p-values less than or equal to 0.05 will be considered statistically significant, while those less than equal to 0.10 will be considered suggestive. Since this trial is the first use of this treatment for this diagnostic indication, no adjustments of p-values for multiple comparisons will be made. Thus, all control of type 1 error is contrast-wise. All confidence intervals will be two-sided with 95% confidence. Mean treatment effect, standard errors, and 95% confidence intervals will be derived from fully adjusted models on outcomes averaged across the treatment period. Cohen's d and p-values will be calculated from fully adjusted models with appropriately transformed outcome variables. For dichotomous drinking outcomes, prevalence rates will be calculated. Odds ratios (ORs) and p-values will be derived from logistic regression models including treatment group.

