### 20.3.2 Analysis of the Primary Endpoint(s)

For Hypothesis 1a, Safety and tolerability, the frequency of adverse events will be analyzed for the entire sample at all time points, tabulated for each treatment group, and compared using chi-squared tests. The safety analysis will be largely descriptive of outcomes for the entire study population. The incidence of AEs will be summarized by system organ class, preferred term, the likelihood of its relationship to the treatment, and severity for each treatment group. Clinical laboratory data will be summarized by type of test. Frequency and percentage of patients whose values fall outside of reference ranges will be presented for each measurement.

For Hypothesis 1b, Alcohol Use. The Primary outcome measure, number of drinks per day, will be analyzed with an MMRM to assess differences in change from baseline. The primary contrast is change from baseline (B1) at week 6 (T8). The model at each time point will include terms for treatment, time and treatment by time interaction as factors and the baseline value for each score as a covariate. Parameter estimation will be based on REML and to begin an unstructured covariate matrix will be used. If the model fails to converge, the form of the covariance matrix will be chosen based on Akaike's Information Criteria, and Schwarz' Bayesian Criterion. Model-based LS means will be obtained for change from baseline to each time point for each treatment group. At each time point, contrasts between CBD and placebo will be obtained. Secondary alcohol use measures will be tested with MMRM sequentially in a closed testing union intersection paradigm in the order listed in section C.8.3. Validity of the p-value will extend until the first test fails to have a p-value smaller than a two-sided alpha of 0.05. The analyses will continue for all measures but the resulting p-value will be nominal.

For Hypothesis 2, PTSD symptoms, the primary outcome measure, total score of the PCL-5, will be analyzed in the same way as the primary outcome for alcohol use. The primary contrast is change from baseline (B1) at week 6 (T8).

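### The plan gives two unreconciled models for the weekly no-heavy-drinking-days endpoint, and the logistic one names no baseline drinking term, which costs power and pulls the odds ratio toward 1

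*Combined protocol and SAP*

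**What the plan says.** Section 4.2.2 lists the "weekly percentage of subjects with no heavy drinking days" among the secondary alcohol endpoints. It defines a heavy day as "four or more drinks for women or five or more drinks for men per drinking day". Section 5.1 uses the same cut-offs for entry and requires "At least 4 heavy drinking days" "in the 30 days prior to screen".

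Two places describe the analysis:

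- Section 20.3.1: "For dichotomous drinking outcomes, prevalence rates will be calculated". It continues: "Odds ratios (ORs) and p-values will be derived from logistic regression models including treatment group". No other term is named. The same paragraph asks for fully adjusted models when it describes mean effects and Cohen's d.
- Section 20.3.2: secondary alcohol measures are to "be tested with MMRM sequentially in a closed testing union intersection paradigm". The MMRM described there carries the baseline value of each score as a covariate. Binary measures are not excepted.

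Section 20.3.6 lists baseline percentage of heavy drinking days among the characteristics compared between groups, so the covariate will be in the data. No section gives its expected mean or spread.

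**The concern.** One binary endpoint falls under two analysis rules that differ in model type, effect measure and covariates. A logistic model yields an odds ratio. An MMRM fitted by REML yields least-squares mean differences, which is not a natural analysis for a yes/no outcome. An analyst following section 20.3.1 as written would leave out the variable that best predicts the result.

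Section 20.3.1 makes effect sizes and response rates the main focus of the analysis, and section 20.4 says the design is meant to inform later confirmatory trials. An odds ratio pulled toward 1 and a weaker comparison of arms both work against that purpose.

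**Working it through.** **Inputs.** From the documents: entry minimum 4 heavy days in 30 (5.1), the same heavy-day definition at entry and in the endpoint (5.1, 4.2.2), and arms of 30 and 18 (20.5.1). Assumed: unchanged drinking, independent days, and a range of baseline frequencies. The plan states no expected rate or power for this endpoint. Its only power figure (20.4) is for a t test of means, so there is no figure to reproduce.

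**1. Dependence on baseline.** With k heavy days per 30, the chance of a week with none is (1 − k/30)^7.

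| k per 30 | Calculation | Chance |
|---|---|---|
| 4 | (26/30)^7 | 36.7% |
| 6 | (24/30)^7 | 21.0% |
| 8 | (22/30)^7 | 11.4% |
| 10 | (20/30)^7 | 5.9% |
| 15 | (15/30)^7 | 0.8% |

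The odds are 0.367/0.633 = 0.580 at k = 4 and 0.0078/0.9922 = 0.0079 at k = 15, roughly a 74-fold difference with no treatment effect. At k = 4 the chance is 32.3% if the seven days are drawn without replacement from the 30, and 39.3% under a Poisson count. It is 42% to 60% if heavy days cluster (assumed within-person correlation 0.05 to 0.30).

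**2. Effect on the odds ratio.** Assume half the participants have k = 4, half have k = 15, and the odds ratio within each half is 3.

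- Placebo rate: (0.3673 + 0.0078)/2 = 0.1875.
- CBD rate at k = 4: 3 × 0.5805/(1 + 3 × 0.5805) = 0.6352.
- CBD rate at k = 15: 3 × 0.00787/(1 + 3 × 0.00787) = 0.0231.
- CBD average: (0.6352 + 0.0231)/2 = 0.3291.
- Treatment-only odds ratio: (0.3291/0.6709)/(0.1875/0.8125) ≈ 2.13.

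The shift from 3 to 2.13 is the known non-collapsibility of the odds ratio. It is not confounding.

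**3. False positives.** In 20,000 simulated no-effect trials of 30 v 18, with baselines mixed over 4, 8, 15 and 25 heavy days, a treatment-only comparison (pooled z test) rejected 5.3% of the time. A likelihood ratio test rejects more often when events are rare, but the cause is sparseness. When every participant has the same event probability, it rejects 7.2%, 8.7% and 10.0% at event rates of 4.5%, 6% and 8.3%. With varying baselines it rejects 7.2% to 9.9%, about the same.

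**4. Power and sparseness.** Baselines were assumed to follow beta distributions truncated at 4 of 30, with means of 12.7 to 17 heavy days. The no-effect weekly rate is then 4.4% to 9.7%. That is 48 × 0.044 = 2.1 to 48 × 0.097 = 4.7 participants in all, and 18 × 0.044 = 0.8 to 18 × 0.097 = 1.7 on placebo. Chance imbalance in baseline shifts the expected difference between arms by up to 5 to 8 points in 95% of randomisations. With heavy days cut by 70% on CBD and 30% on placebo, adding log baseline heavy days raised single-week power by 7 to 9 points with a likelihood ratio test (for example 53% to 61%). With penalised likelihood the gain was about 3 to 6 points, with no rise in false positives.

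**5. Whether the MMRM covariate would serve.** Section 20.3.2 adjusts for the baseline value of each score. If that means the same yes/no indicator over the entry look-back, section 5.1 makes it identical for everyone and it adjusts for nothing. The covariate has to be a frequency.

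**The case against.** The strongest defence is that naming treatment group in section 20.3.1 need not be exhaustive, and that section 20.3.2 already supplies a baseline covariate for secondary alcohol measures. This is also a secondary endpoint in a 48-person pilot that does not expect significance unless effects are very large. Section 20.1 promises a formal SAP before database lock and unblinding. All of that is fair. It limits the weight of the point and makes it easy to settle, but it does not say which model applies.

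A reader might infer something stronger. Four heavy days in 30 is 7 × 4/30 = 0.93 per week, so the entry cut-off might seem to coincide with the endpoint, letting chance weeks manufacture responders and false positives. The documents do not support this:

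- Four in 30 is a minimum. The 37% applies only to someone exactly at it, and no baseline distribution is given.
- An average of 0.93 per week and a count of zero in seven days are different quantities.
- The endpoint is a group percentage for each week. Nothing labels a person a responder after one clean week.
- Chance weeks occur in both randomised arms, and random baseline imbalance is already part of the test's sampling error.
- Excess rejection appears with a likelihood ratio test in sparse data, whether or not baselines vary. The plan does not specify that test for this model.

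**Conclusion.** The point holds as a gap in specification with a modest cost. Sections 20.3.1 and 20.3.2 give different models for one binary endpoint, and the model written for binary outcomes names no baseline term. Baseline frequency moves the no-effect chance of a clean week from 37% to under 1% between 4 and 15 heavy days in 30. Leaving it out therefore loses about 3 to 9 points of single-week power and shrinks the odds ratio (3 to about 2.13 in the two-group illustration). The comparison between arms stays valid.

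The weekly chances assume independent days. The power figures rest on assumed baseline distributions and an assumed 70% v 30% cut in heavy days, and they describe one week. An analysis of all weeks could gain more or less.

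**What to change.** In sections 20.3.1 and 20.3.2, or in the formal SAP:

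- State that the no-heavy-drinking-days endpoint is analysed by one logistic model and is excepted from the MMRM. Say which week it uses, or specify a repeated-measures logistic model if all treatment weeks are used.
- Include baseline heavy drinking days from the Timeline Followback as a covariate (percentage or log count), with its look-back window stated.
- Make penalised likelihood the planned fitting method, since a week may have very few events.
- Report the placebo-arm rate by baseline frequency, so that readers can see how much of it unchanged drinking would produce.
- Optionally, add a sensitivity analysis counting two consecutive weeks without a heavy day. Section 20.3.10 already uses a two-week persistence rule for the exploratory onset analysis. For an unchanged participant at the entry minimum, a specified pair of weeks has a chance of 0.367² = 0.135.

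This costs wording only and needs no new data. The downside is one more parameter in a sparse model.

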#### AUD-related measures

The Penn Alcohol Craving Scale (PACS) [79] will be used to assess craving. This scale has 5 Likert-scaled items with excellent internal consistency and evidence of predictive, construct, and discriminant validity. Self-efficacy will be assessed using the Alcohol Abstinence Self-Efficacy Scale (AASE) [81], a self-report questionnaire which has been used widely in the alcohol treatment research, both as a predictor of outcome and as a patient-treatment matching variable [82]. Craving, self-efficacy, and alcohol use will be assessed before treatment (baseline), week 1, week 6, and at one week following the completion of treatment. Mood and Anxiety will be measured with the Beck Anxiety Inventory (BAI) [99] and Beck Depression Inventory-II (BDI-II) [100] scales at baseline, treatment weeks 1, 4 and 6, and at one week following treatment completion.

Risk of suicidality will be assessed by a licensed study provider using the Columbia-Suicide Severity Rating Scale (C-SSRS) [98] as part of each study visit.

#### **PTSD-related measures**

The PCL-5 will be administered at baseline, weeks 2, 4, 6 and 7. In addition to the PCL-5 score (primary PTSD endpoint), childhood trauma (child abuse and neglect) will be assessed at baseline using the self-report Childhood Trauma Questionnaire (CTQ) (28 item).

#### Traumatic stress and cue response task

The Cue and Stress Response Task will be performed at the 4- week time-point using methodology developed in [name]'s lab, similar to those in used in past studies with alcohol dependent patients [84]. [name] will provide consultation on the implementation of these methods. Briefly, imagery scripts will be developed at baseline. Traumatic stress imagery scripts will be based on a recent highly stressful traumatic situation the participant has experienced unrelated to alcohol use. Alcohol cue scripts will be derived from a recent event that included alcohol-related stimuli and led to alcohol use. Neutral or relaxing scripts will also be developed. All scripts will be developed by obtaining specific details of stimulus and response, including contextual details, cognitive and verbal content, affective experience, and bodily sensations. These details form the basis of a 5-minute imagery script, which will be developed for each of the three conditions. Imagery sessions will be structured with a 5-minute pre-imagery period, a 5-minute imagery period, and a 5-minute recovery period. Pulse, skin conductance, heart rate variability, and blood pressure will be monitored during each imagery session with an ADInstruments PowerLab 4/30 Galvanic Skin Response device and a Contec Patient Monitor. In Human laboratory studies with CBD, skin conductance and amygdala activation were reduced by CBD in a closely correlated manner [52], suggesting threat-related sympathetic arousal may serve as a proxy for amygdala activation [53].

Participants will complete Likert scale ratings of vividness, craving, anxiety, and the 30-item Differential Emotion Scale [84] following each of the three periods. After each condition, a progressive relaxation procedure will be implemented to facilitate return to baseline of vital signs, craving and anxiety, an approximate period of 10 minutes, as shown in previous research from the [name] lab [84]. The entire imagery protocol will take 120 minutes. The order of the sessions will be randomized and counterbalanced among participants. The task will be completed at T6 (the end of 4 weeks of treatment with 600mg daily). At this point, we expect steady-state plasma CBD levels to have been reached.

#### Plasma CBD, THC and anandamide levels

Measurement of circulating levels of CBD, THC, Delta-9 THC, 11-Hydroxy Delta-9 THC and Delta-9 Carboxy THC will be obtained from CBD-treated participants at baseline (pre-CBD levels), following 45 minutes (T1-

45min post-CBD levels), 1 day (T2-45min post-CBD levels), 1 week (T3-45min post-CBD and pre-CBD levels), 2 weeks (T4-45min post-CBD and pre-CBD levels), 4 weeks (T6-45min post-CBD and pre-CBD levels), 6 weeks (T8-45min post-CBD and pre-CBD levels), and 7 weeks (T9- pre-CBD levels) after the first CBD vs. placebo dose. Anandamide levels will be obtained from both CBD- and placebo-treated participants at the aforementioned timepoints. All three levels (CBD, THC and anandamide) will be determined via High Performance Liquid Chromatography/Tandem Mass Spectrometry (LC-MS/MS) by the Nathan Kline Institute.

## Psychomotor and subjective effects of CBD

Basic motoric and cognitive function will be evaluated throughout treatment with several established field sobriety tests, including a walk-and-turn task, one-leg stand, Romberg's test, finger-finger test, and counting backwards [85]. The Addiction Resource Center Inventory (ARCI), 49-item version [86], will be used as a measure of the intoxicating effects and abuse potential of CBD. Breath Alcohol Concentration (BAC) will also be measured to ensure participants are not under the influence of alcohol during administration of these tasks.

## **Cognitive Function**

Several established neuropsychiatric and cognitive tasks will be administered to evaluate the impact of CBD vs. placebo treatment on cognitive domains potentially affected by CBD and/or THC. The Rey Auditory Verbal Learning Task (RAVLT) will be used to assess episodic memory [87], the Mental Rotation Task (MRT) will evaluate visuospatial ability [88, 89], a Time Reproduction Task (TRT) will measure encoding and retrieval of time intervals [67] and several WM Span tasks (OSpan, RSpan, SymSpan, RotSpan) will measure working memory capacity [90, 91]. Cognitive function will be measured at day 1 (T2) and at the end of treatment (T8).

